9.6.5 Exploratory Variables

The exploratory variables will be summarized by descriptive statistics by treatment group in the mITT. No statistical analyses are planned. The list of variables includes the change from Baseline to Week 24 (where applicable) for the following:

- 1. Number of hours per day spent in the asleep state.
- 2. Dyskinesia as measured by questions 32, 33 and 34 of UPDRS Part IV.
- 3. Falls as measured by question 13 on UPDRS Part II.
- 4. Responder analysis of number (%) of patients with ≥ 1.0 h improvement in OFF time (evaluated at Week 24).
- 5. Responder analysis of number (%) of patients with ≥ 2.0 h improvement in OFF time (evaluated at Week 24).
- 6. Percent change in total levodopa equivalent dose.
- 7. Percent change in the number of hours per day spent in OFF state.
- 8. Percent change in the number of hours per day spent in ON state without troublesome dyskinesia.
- 9. Percent change in the number of hours per day spent in ON state with troublesome dyskinesia.
- 10. Scales for Outcomes in Parkinson's Disease-cognition (SCOPA-cog) score.
- 11. Fall questionnaire score.
- 12. Number of hours per day spent in the OFF state in the sub-population of subjects taking levodopa and only one additional concomitant anti-PD medication.
- 13. Number of hours per day spent in the OFF state in the sub-population of subjects taking levodopa and two additional concomitant anti-PD medications.
- 14. Number of hours per day spent in the OFF state in the sub-population of subjects taking levodopa and three additional concomitant anti-PD medications.

9.6.6 Adjustment for Multiplicity

9.6.6.1 Tozadenant 120 mg BID vs. Placebo and tozadenant 60 mg BID vs. Placebo

All analyses of the primary and two key secondary endpoints will focus on the comparison of tozadenant 120 mg BID vs. placebo followed by tozadenant 60 mg BID vs. placebo. The following six comparisons will be conducted using sequential testing with a fixed sequence, which controls the family-wise error for multiple comparisons at an alpha level of 0.05 (two-tailed):

- 1. Comparison of tozadenant 120 mg BID vs. placebo using the primary endpoint (change from baseline to Week 24 in the number of hours per day spent in OFF state).
- 2. Comparison of tozadenant 120 mg BID vs. placebo using the first key secondary endpoint (Change from baseline to Week 24 in the number of hours per day spent in good ON time, defined as the sum of ON time without dyskinesia and ON time with non-troublesome dyskinesia).
- 3. Comparison of tozadenant 120 mg BID vs. placebo using the second key secondary endpoint (Change from baseline to Week 24 in UPDRS Parts II + III total score).

4. Comparison of tozadenant 60 mg BID vs. placebo using the primary endpoint (change from baseline to Week 24 in the number of hours per day spent in OFF state).

CONFIDENTIAL

- 5. Comparison of tozadenant 60 mg BID vs. placebo using the first key secondary endpoint (Change from baseline to Week 24 in the number of hours per day spent in good ON time, defined as the sum of ON time without dyskinesia and ON time with non-troublesome dyskinesia).
- 6. Comparison of tozadenant 60 mg BID vs. placebo using the second key secondary endpoint (Change from baseline to Week 24 in UPDRS Parts II + III total score).

Testing will begin with tozadenant 120 mg BID vs. placebo for change from baseline to Week 24 in the number of hours per day spent in OFF state. If the p-value is less than or equal to an α =0.05, then the result is considered statistically significant and testing will proceed to the next comparison, and so forth. Testing will stop with the first adjusted p-value > 0.05 and that comparison, as well as any comparison later in the sequence will be considered not statistically significant.

The adjusted p-values p'_i for i=1 to 6 will be calculated by taking the maximum of the raw p-value (p_i) from the statistical test and the adjusted p-value (p'_{i-1}) from the prior test, as shown below:

```
\dot{p}_1 = p_1 

\dot{p}_2 = \max(\dot{p}_1, p_2) 

\dot{p}_3 = \max(\dot{p}_2, p_3) 

... 

\dot{p}_6 = \max(\dot{p}_5, p_6)
```

p-values from the analyses of all other efficacy outcomes will be reported as nominal, with no adjustment for multiplicity.

9.6.7 Tozadenant Plasma Concentrations

During Part A of the study, blood samples will be collected for determination of plasma tozadenant concentrations at baseline before dosing, at weeks 2, 6 12, 18 and 24 (end of dosing). In addition, samples may be taken at an unscheduled visit and at an early termination visit.

Plasma concentration data will be presented for all subjects in the safety population by treatment group, including placebo. In all calculations, including placebo-group subjects, zero (0 ng/mL) will be substituted for concentration below the quantification limit (BLQ; equivalent to <5 ng/mL) of the assay.

Elapsed time between dosing and plasma sampling will not be tightly controlled and is expected to vary considerably between patients. Summary statistics for tozadenant blood concentrations (number of sample analyzed, number of BLQ values, minimum, and maximum) will be presented by sampling occasion. For treatment visits when 2 consecutive plasma samples are analyzed (weeks 2 and 24), the 2 values will be presented separately.

All data collected on the tozadenant blood concentrations will be included in the data listings.

Separate population analyses on the data from this study alone or combined with data from other studies as deemed appropriate may be performed and reported separately.

9.6.8 Pramipexole Plasma Concentrations

During Part A of the study, blood samples will be collected for determination of plasma pramipexole concentrations at baseline before tozadenant dosing, and at weeks 2 and 24 (end of tozadenant dosing). In addition, samples may be taken at an unscheduled visit and at an early termination visit.

Plasma concentration data will be presented for all subjects in the safety population by treatment group, including placebo. In all calculations, zero (0 ng/mL) will be substituted for concentration below the quantification limit (BLQ; equivalent to <5 ng/mL) of the assay.

Elapsed time between dosing and plasma sampling will not be tightly controlled and is expected to vary considerably between patients. Summary statistics for pramipexole blood concentrations (number of sample analyzed, number of BLQ values, minimum, and maximum) will be presented by sampling occasion. Since 2 consecutive plasma samples will be analyzed on each sampling day, the 2 values will be presented separately.

All data collected on the pramipexole blood concentrations will be included in the data listings.

Separate population analyses on the data from this study alone or combined with data from other studies as deemed appropriate may be performed and reported separately.

9.7 Safety Analyses

9.7.1 Adverse Events

A summary of TEAEs including the number of events reported, the number and percentage of subjects reporting at least 1 AE, the number and percentage of subjects discontinuing due to an AE, the number and percentage of subjects with at least 1 serious adverse event, and the number and percentage of deaths will be presented by treatment group and combined tozadenant group.

A breakdown of the number and percentage of subjects reporting each TEAE, categorized by SOC and PT coded according to the MedDRA dictionary, by treatment group and combined tozadenant group. Note that counting will be by subject, not event and subjects are only counted once within each SOC or PT.

A further tabulation of these data will be presented by treatment group and combined tozadenant group for TEAEs that are related to study drug, as defined by those AEs with relationship to study drug recorded on the eCRF as Possible or Probable. Events that are unrelated or remotely/Unlikely related will not be considered "related" for the Causality assessment. An AE with a missing relationship will be considered as having a relationship to study drug of possible. Subjects with multiple events within a particular SOC or PT will be counted under the category of their most drug-related event within that SOC or PT.

A summary of events reported, categorized by severity (mild, moderate, severe and very severe) will also be provided by treatment group and combined tozadenant group. AEs with missing or unknown severity will be considered severe. Subjects with multiple events within a particular SOC or PT will be counted under the category of their most severe event within that SOC or PT.

A summary of adverse events leading to discontinuation will be provided, grouped by system organ class and preferred term by treatment group and combined tozadenant group.

All AEs (including non-treatment-emergent events) recorded on the eCRF will be listed along with other information such as duration, severity, action taken, and perceived relationship to study drug.

9.7.2 Deaths and Serious Adverse Events

Serious TEAEs will be summarized by the number and percentage of subjects reporting each AE, categorized by SOC and PT coded according to the MedDRA dictionary, by treatment group and combined tozadenant group. Note that counting will be by subject, not event and subjects are only counted once within each SOC or PT.

9.7.3 Laboratory Data

Clinical laboratory values will be evaluated by subject for each laboratory parameter. Laboratory test results will be reported and they will be assigned a LNH classification by each laboratory according to whether the value was below (L), within (N), or above (H) the laboratory reference range. Reference (normal) ranges for laboratory parameters provided by each of the central labs will be included in the clinical study report for this study and will be used for shift tables. Summary tabulations of the continuous clinical laboratory (hematology, chemistry, thyroid function (TSH, free T3 and free T4), and urinalysis) data (n, mean, standard deviation, median, minimum, and maximum) for baseline, each scheduled visit (defined in Table 1), and change from baseline for laboratory data will be provided for the safety analysis set by treatment group. The baseline measurement will be defined as the last assessment prior to the first dose of study drug, including any repeated or unscheduled evaluations. Quantitative urinalysis data will only be listed.

An ANOVA will be performed on change from baseline of last on treatment observation for all continuous clinical laboratory tests, with treatment group as a class variable and within the ANOVA, each tozadenant treatment group will be compared to placebo through estimate statements. The treatment difference from placebo and corresponding p-value will be reported.

Shift from baseline to each scheduled visit will be summarized for the safety analysis set by treatment group for hematology, chemistry, thyroid, and urinalysis variables that are assigned a LNH classification. In addition, shift from baseline to worst post-baseline for the same laboratory variables will be presented based on the LNH classification.

The continuous laboratory hematology, thyroid function (TSH, free T3 and free T4), and urinalysis will have the worst post-baseline value plotted versus the baseline visit for the safety analysis set. The minimum lower limit of normal range and maximum upper limit of normal range amongst laboratories will be drawn in on the x and y axis as vertical lines. The reference normal range will be determined from the normal ranges of all the central laboratories.

All laboratory data will be included in the data listings.

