- 5. Is a congenital anomaly or birth defect, i.e., an adverse event (AE) that occurs in the child or fetus of a patient exposed to a study drug prior to conception or during pregnancy.
- 6. Is an important medical event, i.e., an event that may not be immediately life-threatening or result in death or hospitalization but, based upon appropriate medical and scientific judgment, may jeopardize the patient or may require medical or surgical intervention to prevent one of the other serious outcomes listed above.
 - Examples of important medical events include, but are not limited to, intensive treatment in an emergency room or at home for allergic bronchospasm, blood dyscrasias, or convulsions. Interruption, discontinuation, or adjustment of dose level of study drug alone will not be considered an intervention that satisfies the definition of important medical event.

Although fulfilling the above listed criteria, the following events are not regarded as being serious for this study:

Hospitalizations for:

- Facilitation of assessments specific to this protocol not associated with any deterioration in condition (e.g., when travel time between a patient's home and the study site would otherwise preclude adequate evaluation).
- Elective or preplanned assessment or treatment for a preexisting condition that has not worsened since initiation of study drug administration.

Any SAE meeting above criteria that occurs during the study or within 4 weeks after the last dose of study drug must be reported within 24 hours (1 working day) by email and/or fax and by completing the AE electronic case report form (eCRF) and the SAE Report Form. Once the AE eCRF is completed designating an AE as serious, an email will be generated to notify and that an SAE has occurred and the information will be transmitted to the designated parties for review.

Confidential Page 6 of 195

Refer to additional SAE reporting instructions in **Section 9.2**.

FINAL, 13 October 2017 TOZ-CL05, Amendment No. 3

CLINICAL STUDY PROTOCOL SIGNATURE PAGE

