- ^u Only for patients concomitantly taking pramipexole: PK blood sample collected for tozadenant will also be analyzed for plasma pramipexole at Baseline (Visit 2, predose). A second PK blood sample for plasma pramipexole concentration will be taken at Baseline at least 45 minutes after the first PK sample is collected.
- Only for patients concomitantly taking pramipexole: PK blood samples collected for tozadenant will also be analyzed for plasma pramipexole concentration including both samples collected at Weeks 2 (Visit 3) and 24 (Visit 7) and Early Termination Visit during Part A. If a tozadenant sample is not being collected at the Early Termination Visit (patient's last dose of IMP was taken more than 7 days before the visit) a PK sample for plasma pramipexole concentration will be collected.
- W Only for patients with potential pramipexole-related AEs: During Part A, in the event of AEs thought to be pramipexole-related (e.g., dyskinesia, hallucinations, delusions, hypotension, somnolence, nausea, vomiting), either noted at the time of a scheduled study visit or an Unscheduled Visit, PK blood sample collected for tozadenant will also be analyzed for plasma pramipexole, i.e., at Week 6 (Visit 4), Week 12 (Visit 5) or Week 18 (Visit 6). If a tozadenant sample is not being collected at an Unscheduled Visit a PK sample for plasma pramipexole concentration will be collected. See Section 8.2.
- If patient has discontinued IMP, perform the Early Termination Visit as soon as possible after the last dose of IMP. Efficacy-related measures (e.g., PD diary, UPDRS, CGI-I, PGI-I, and CGI-S) will not be completed at an Early Termination Visit if patient stopped taking study drug more than 24 hours prior to the assessment of the measures during the Early Termination Visit. If patient took the last dose of IMP 28 or more days prior to the Early Termination Visit, a Post-Early Termination Safety Follow-Up Visit (Section 6.2.35) is not required.

Confidential Page 36 of 195

Table 1.1: Part A – Schedule of Events/ Evaluations for Hematology Monitoring

TOZ-CLO5 PART A: D	OUBLE-F	BLIND PH	Weekly monitoring b (if required)				
	dy Week	4 (±3 d)	8 (±3 d)	(24 weeks 10 (±3 d)	16 (±3 d)	22 (±3 d)	(ii requireu)
Assessments St	udy Visit	V3.5	V4.3	V4.8	V5.5	V6.5	A97
Laboratory test: hematolo	gy ^a	X	X	X	X	X	X
Recording of AEs							X
Recording of concomitant Anti-PD medications	t and						X
eCRF completion		X	X	X	X	X	X

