Eligible patients will be randomized in Part A to receive 1 of 2 tozadenant doses (60 mg BID or 120 mg BID) or placebo in a ratio of 1:1:1. Blinded IMP will be dispensed to patients at each study visit and will be taken BID (approximately 12 hours apart) for 24 consecutive weeks. Patients will return to the study site for evaluation at Weeks 2, 6, 12, 18, and 24. Patients will be contacted by telephone before the start of each 3-day PD diary completion period to be reminded to complete the diary for 3 consecutive days prior to their next scheduled visit. Patients will also be scheduled for a laboratory draw (hematology only) at Weeks 4, 8, 10, 16 and 22. Unscheduled Visits can be arranged as considered necessary by the investigator (see Section 6.2.34). In the event of Early Termination during Part A, patients will be asked to complete an Early Termination Visit as soon as possible (see Section 6.2.32) and then return 28 ± 3 days after their last dose of IMP for a Post-Early Termination Safety Follow-Up Visit (Section 6.2.35). Blinded safety data from the double-blind phase (Part A) will be provided to the Data and Safety Monitoring Board (DSMB), at a frequency specified by the DSMB charter, for ongoing monitoring of safety and detection of any trends. If requested by the DSMB, the DSMB statistician will provide unblinded safety data to the DSMB on a per needed basis, to enable a fully informed review.

During Part B, scheduled study visits for evaluations will take place at Weeks 26, 30, 36, 48, 60, and 76, and at Week 80 (Safety Follow-Up Visit). Patients will also be scheduled for a laboratory

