- 10. Patients with an absolute neutrophil count less than 1000/mm³ (or 1.0 x 10E9/L).* Following study drug discontinuation, these patients will require weekly hematology measurements until the WBC and/or ANC returns to 75% of the baseline value (Visit 2). Assess for adverse events and concomitant medication changes and record as an unscheduled visit. Discuss with medical monitor to assure that the patient is discontinued from study drug and that the appropriate follow up safety measures are taken.
 - * Any patient experiencing a decline in absolute neutrophil count (ANC) and/or white blood cells (WBC) by 50% from baseline (Visit 2) will require a weekly hematology measurement until the WBC and/or ANC returns to 75% of the baseline value. The patient will continue with dosing during the weekly hematology follow-up. Assess for adverse events and concomitant medication changes and record as an unscheduled visit. If the WBC and/or ANC returns to 75% of baseline, the patient should return to routine evaluations as outlined in the Schedule of Events/Evaluations. Discuss with medical monitor.

All patients who discontinue prematurely from the study will be requested to return to the study site as soon as possible to complete the safety and efficacy evaluations outlined for an Early Termination Visit in the Schedule of Events/Evaluations (**Table 1** and **Table 2**) and in **Sections 6.2.32** and **6.2.33**. The Early Termination Visit should be done under IMP treatment, if possible. After Early Termination, the patient will also be asked to return for a Safety Follow-Up Visit to be scheduled 28 (±3) days after their last dose of IMP, unless the Early Termination Visit itself occurred 28 or more days after the last dose of IMP (see **Section 6.2.35**).

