1 INTRODUCTION

TOZ-CL05 will include a 24-week double-blind phase (Part A) followed by a 52-week open-label phase (Part B). This statistical analysis plan (SAP) describes the statistical methods to be used during the reporting and analyses of data collected under Part A (double-blind phase) of Biotie's Protocol TOZ-CL05. The SAP for Part B (open-label phase) will be submitted at a later date. The SAP was developed to support Biotie's Special Protocol Assessment (SPA).

This SAP should be read in conjunction with the study protocol and the SPA document. This version of the plan has been developed using final protocol Amendment No. 1, dated 19 May 2015.

Table, figure and listing (TFL) shells will be developed at a later date.

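### The SAP's continuous by-visit laboratory summaries leave out 5 of the 10 scheduled post-baseline Part A hematology draws, and no planned table counts patients who reach the protocol's own ANC and WBC limits

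*SAP*

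**What the plan says.** **Versions.** SAP section 1 states: "This version of the plan has been developed using final protocol Amendment No. 1, dated 19 May 2015". The SAP itself is v1.0 of the same date. The protocol supplied is headed "FINAL, 13 October 2017 TOZ-CL05, Amendment No. 3".

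**Draws.** Protocol 3.1 says "Patients will return to the study site for evaluation at Weeks 2, 6, 12, 18, and 24" and then "Patients will also be scheduled for a laboratory draw (hematology only) at Weeks 4, 8, 10, 16 and 22". The first set is in protocol Table 1. The second is in Table 1.1, whose title includes "Evaluations for Hematology Monitoring" and whose footnote sends the reader to 4.3.2 for weekly monitoring. SAP section 3 and SAP Table 3-1 contain only the first set.

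**Laboratory outputs.** SAP 9.7.3 plans:
- continuous summaries at baseline and at "each scheduled visit (defined in Table 1");
- an ANOVA on the last on-treatment value;
- shift tables to each scheduled visit and to the worst post-baseline value, by low/normal/high class;
- a plot of worst post-baseline value against baseline;
- listings of everything.

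**Limits.** Protocol 4.3.2 requires discontinuation when ANC is below 1000/mm3. It requires weekly hematology, with dosing continued, for "Any patient experiencing a decline in absolute neutrophil count (ANC) and/or white blood cells (WBC) by 50% from baseline" (Visit 2). SAP 9.7.3 names neither limit.

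**The concern.** The extra draws and the two limits form the protocol's hematology monitoring scheme. A reader of the Part A report will want to know how many patients in each arm crossed each limit, and what the counts looked like at every scheduled draw. Followed as written, the supplied SAP gives by-visit statistics at half of the post-baseline draws and leaves the threshold counts to be made by hand from listings after unblinding. Efficacy conclusions are not touched. What is at stake is how completely and clearly the hematology safety data are reported.

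**Working it through.** The plan states no figure to reproduce here. The check is a count of draws and a comparison of texts.

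**1. Draws covered by the by-visit summaries**
- Protocol Table 1 and SAP Table 3-1, post-baseline hematology: Weeks 2, 6, 12, 18, 24 = 5 draws.
- Protocol Table 1.1: Weeks 4, 8, 10, 16, 22 = 5 draws.
- Total 5 + 5 = 10. Left out: 5/10 = 50%. If Screening and Baseline are counted as well: 5/12 = 42%.
- Gaps between tabulated draws, from Week 0: 2, 4, 6, 6, 6 weeks with Table 1 alone; 2, 2, 2, 2, 2, 2, 4, 2, 4, 2 weeks with both tables. The longest gap falls from 6 weeks to 4.

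**2. Against the protocol's own analysis text**
Protocol 11.5.1 asks for laboratory descriptive statistics and change from baseline at every time point measured, and for shift tables to each visit by treatment group. The SAP's restriction to Table 1 visits does not deliver the first of these for hematology.

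**3. Whether low/normal/high can yield the two counts**
- *ANC below 1000/mm3.* Every value under the reference range falls in one class. Assuming that 1000/mm3 lies below the laboratory's lower limit of normal (LLN), which the documents do not give, patients below 1000 share a cell with patients between 1000 and the LLN.
- *50% fall.* For baseline value B, a fall of exactly 50% gives B/2. This is still classed normal whenever B/2 ≥ LLN, that is, B ≥ 2 × LLN. Such a patient meets the protocol limit and is never classed low. How many such patients there could be depends on the reference range.

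**4. Whether the other outputs supply the counts**
- *By-visit minimum:* shows that at least one patient was below 1000/mm3 at a tabulated visit, not how many.
- *Worst-value shift table:* low/normal/high only. The SAP does not say whether Table 1.1 or unscheduled draws feed it. Weekly monitoring draws are recorded as unscheduled visits, so this matters.
- *Worst-value plot:* shows depth and proportional fall on a continuous scale, but with reference lines at the normal range only and no by-arm display specified.
- *ANOVA on the last on-treatment value:* patients with a 50% fall continue dosing and return to routine evaluation at 75% of baseline, so a fall that has recovered need not show.
- *Withdrawal reasons (SAP 9.1) and adverse events (SAP 9.7.1):* may show some cases below 1000/mm3, but no ANC category is named. A laboratory value becomes an adverse event only if judged clinically significant (protocol 11.5.1).
- *Listings:* hold every value, uncounted.

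**5. The SAP's practice elsewhere**
SAP 9.7.4 counts systolic pressure ≥160 and diastolic ≥100 mmHg, and SAP 9.7.10 counts QTcF >500 msec and change >60 msec. These match or closely track the blood pressure and QTcF withdrawal limits in protocol 4.3.2. ANC and WBC have limits in the same section but no such count.

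**The case against.** The best reply is that most of this is already reported and the rest is an outdated cross-reference. The restriction to Table 1 visits is written into one output only. The worst-value shift, the plot, the ANOVA and the listings carry no such limit, and a natural reading of worst post-baseline takes in every draw. The SAP says it should be read with the protocol, and protocol 11.5.1 already calls for every measured time point. Severe cases must be discontinued, so they reach the withdrawal tables, and often the adverse event tables, by arm. Table shells were deferred, and a later SAP may exist.

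Much of this stands, and it rules out three stronger readings that a reader might infer:
- *That the laboratory tables as a whole omit half the draws.* Only the continuous by-visit summaries are expressly limited. The by-visit shift tables are affected only if scheduled visit has the same meaning there.
- *That the plan cannot distinguish a very low ANC from one just under normal, or loses every nadir that recovered.* That is true of the low/normal/high cells and can be true of the last-value ANOVA. The minima, plot and listings carry actual values, and the worst-value shift would record a recovered low value as low if the draw is included.
- *That Amendment 3 introduced these draws and limits.* The revision history is not in the supplied text. Their absence from a SAP built on Amendment 1 fits a later addition but does not show which amendment made it.

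What the reply does not meet is the missing count. None of the outputs it names gives the number of patients per arm meeting either limit. Pointing to 11.5.1 confirms that the two documents disagree; it does not tell the programmer which to follow.

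**Conclusion.** The point holds in this limited form. In the supplied SAP, the continuous by-visit laboratory summaries cover 5 of the 10 scheduled post-baseline Part A hematology draws, in conflict with protocol 11.5.1. Of the protocol's two ANC/WBC limits, none is counted in any planned table; other outputs give partial coverage only. This is a reporting gap in the safety analysis that should be closed before unblinding. It is not a flaw in data collection or in the efficacy analysis.

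The conclusion assumes that SAP v1.0 is the version in force and that Table 1 in SAP 9.7.3 means protocol Table 1 or its copy, SAP Table 3-1; both list the same hematology weeks. The remark about shared low cells also assumes an LLN above 1000/mm3. The absence of counts does not depend on that.

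**What to change.** Update SAP 9.7.3 to the current protocol:
1. Include the Table 1.1 draws (Weeks 4, 8, 10, 16, 22) in the by-visit hematology summaries and shift tables, and add them to SAP section 3.
2. State that worst post-baseline values use all scheduled and unscheduled draws.
3. Tabulate by arm the number (%) of patients with any post-baseline ANC below 1000/mm3, and with any fall of at least 50% from Visit 2 in ANC or WBC. Name the baseline explicitly: the protocol limit uses Visit 2, whereas SAP 9.7.3 uses the last assessment before first dose, including repeats.

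The counts use limits the protocol already sets; no clinical rule changes. The cost is a SAP update and about two tables, with no new data.
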